15.2 Power Analysis: For the power analysis for the primary analyses, we calculated the minimum detectable effect size (MDES) assuming $n = 200$, a $\alpha = .05$, and power = .80 with 12 covariates in our model. Power was estimated in R (R Core Team) using the pwr library (Champely, 2018). A power analysis was performed to quantify the minimum detectable effect size (f^2) for a three-way interaction between social buffering condition, sex, and pubertal stage within a multiple regression model controlling for the 12 covariates, all two-way interactions, and the main effects (the most complex model considered in our primary analysis, see Equation 1 below). Assuming these conditions, we should be able to detect an f^2 of 0.056. In other words, adding the three-way interaction to a model containing the covariates and all lower order interactions and main effects, the three-way interaction would need to explain an additional 5.6% of the variability to be detected. This falls between Cohen's criteria for a small ($f^2 = .02$) and medium effect ($f^2 = .15$) (Cohen, 1988). With a sample size of 200, even if we lose 40 of the participants to movement artifact for the imaging analyses, assuming all the previous conditions but a sample size of 160, we will still have an f^2 of .070, or still within a small-medium effect size. As the number of covariates decreases, the size of the MDES will decrease. Therefore, this represents a conservative estimate of the power for our primary analyses as we are likely to have fewer covariates in our models

and will use multiple imputation to correct for missing data. For the two-way interaction and main effects models, described below, the power will be larger than these reported values as the models will be simpler.

15.3 Statistical Analysis of MRI and non-MRI Outcome Variables:

The following is a list of the analyses that we will perform on the outcome measures. They are classified as to whether they are the primary or mediational analyses. All statistical analyses will be performed in R.

The primary analyses will consist of a series of multiple regression models. For each dependent variable, variation in neural activity, cortisol, and physiological responses, we will begin by testing the three-way interaction between social buffering condition, sex, and pubertal stage for all outcomes. If the three-way interaction is not significant, we will then examine all two-way interactions. If the two-way interactions are not significant, we will then examine main effects only models. If the three-way interaction is significant, we will not examine any other model. If condition is significant as an interaction or as a main effect, we will examine all pairwise comparisons using Tukey's Honestly Significant Difference test.

Multiplicity of testing. We will correct for multiple comparisons using the Benjamini-Hochberg (BH) correction. The BH method works by controlling the false discovery rate, and relative to the Bonferroni's correction is more powerful, while still adequately protecting against Type I error (Williams, Jones, & Tukey, 1999).

Mediational Analysis. When changes in activity of brain regions differ by condition or condition by pubertal status and we also see condition or condition by pubertal status differences for cortisol or physiological measures, then we will examine whether brain activity differences mediate the neuroendocrine or physiological differences. This will be examined using path analysis, while controlling for covariates identified in the preliminary covariate analysis, and will be estimated using the lavaan package in R (Rosseel, 2012).

The significance of all indirect effects will be assessed using bias-corrected 95% confidence intervals (Efron & Tibshirani, 1986), where confidence intervals that are non-overlapping with zero will be considered significant.

Power Analysis for the Mediational Analysis: To assess power to detect mediation, we performed a Monte Carlo-based power analysis using simulated data. We varied the parameter values to roughly correspond to Cohen's criteria for small, medium, and large effects. This resulted in a total of 27 conditions, which we examined at our target sample size of 200. Each

condition was replicated 2000 times and we calculated empirical power, which we defined as the proportion of times out of 2000 where we rejected the null hypothesis at $\alpha = .05$. Given the exploratory nature of this analysis and to simplify the simulation for the power analysis, we omitted covariates and did not vary the effects for the other condition contrasts (i.e., they were always fixed to 0). Next, we fit a path model using the lavaan package in R.

Our findings suggest that in order to detect mediation, the effect of condition on the mediator must be large and the effect of the mediator on the outcome must be medium or large. In addition, if the effect of condition on the outcome is not large, but small or medium sized, then we will be underpowered and would likely conclude complete mediation, when mediation may only be partial or non-existent. Based on this power analysis, it is likely that the MDES for the moderated mediation models will need to be at least medium to large as well.

Missing data. Because we will replace participants who do not come in for session 2 after doing session 1 (which is rare in our experience), we should have 150 completed participants. Missing data, however, could arise from problems in obtaining good imaging data. Participants also often fail to fully complete questionnaires and/or refuse to provide information on household income. If there is missingness in any of the dependent or independent variables, multiple imputation will be used (Little & Rubin, 2014; Peng, Harwell, Liou, & Ehman, 2006; Schafer & Graham, 2002). Variables related to the missingness and the variables missing data will be included in the missing data model. In the event that missingness is not at random (MNAR), we will investigate the use of models for non-ignorable missing data.

- 15.4 Data Integrity: Biospecimen data will be assayed in labs that have standard quality control procedures. MRI data reviewed for raw data quality and artifact detection.

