15.0 Statistical Considerations

15.1 Data Analysis Plan:

Preliminary Analyses to Determine Covariates Needed for Primary Analyses.

The purpose of collecting data on potential covariates is to identify variables

that are correlated with both the independent variable (social buffering condition, sex, pubertal stage) and the primary outcome measures. Those covariates that are associated with the independent and outcome variables will be controlled for in the primary analyses. Those that are not will be used to describe the sample, but will not need to be included in the analyses to obtain unbiased estimates. For each potential covariate, we will conduct correlations or t-tests with pubertal stage, and t-tests, ANOVAs, or chi-square tests (as appropriate) with sex and condition. If data do not confirm to modeling assumptions, we will use nonparametric analogs instead.

Preliminary Analyses of Imaging Data to Yield Primary Outcome Measures: fMRI data will be analyzed in FSL software (version 6.0.1) to generate voxel-wise contrast maps. Mean signal values will be extracted from these maps in a priori regions of interest for every participant using the methods described below. These preliminary analyses are used to generate the fMRI outcome variables of interest. The values of these outcome variables for each participant will be used in the general statistical analyses described in the next section. In total, these preliminary analyses will yield 6 primary task-related outcome variables, and 6 primary connectivity-related outcome variables.

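### The detectable effects in Section 15.2 assume one test at an unadjusted .05, but Section 15.3 tests all outcomes with a Benjamini-Hochberg correction, so the stated 80% power is not that of the planned decision rule

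*Combined protocol and SAP*

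**What the plan says.** Section 15.2 sets the conditions of the calculation: "assuming $n = 200$, a $\alpha = .05$, and power = .80 with 12 covariates in our model". The effect powered is "for a three-way interaction between social buffering condition, sex, and pubertal stage within a multiple regression model", and the tool is named: "Power was estimated in R (R Core Team) using the pwr library (Champely, 2018". The result is "Assuming these conditions, we should be able to detect an f^2 of 0.056". For a loss of 40 scans to movement, "assuming all the previous conditions but a sample size of 160, we will still have an f^2 of .070". The section concludes that "this represents a conservative estimate of the power for our primary analyses", on two grounds: fewer covariates are likely, and missing data will be imputed. It does not mention multiplicity.

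Section 15.3 starts with the three-way interaction for every dependent variable (neural, cortisol and physiological) and moves to simpler models if it is not significant. Tukey's method handles the pairwise condition contrasts. The multiplicity paragraph then says: "We will correct for multiple comparisons using the Benjamini-Hochberg (BH) correction". It defines neither the family of tests nor q.

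On the number of outcomes, Section 15.1 says that "these preliminary analyses will yield 6 primary task-related outcome variables, and 6 primary connectivity-related outcome variables". Section 3.1 also lists salivary cortisol, heart rate, respiration and skin conductance as primary.

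**The concern.** The power statement is offered for the primary analyses as a whole, but it is computed for a single test compared with .05. Under BH, a p-value must fall below a threshold between .05/m and .05, where m is the number of tests in the family. The threshold depends on how many other tests in the family are also small. Unless every test in the family is rejected, the working threshold is below .05 and power at the stated effect is below the unadjusted figure.

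At stake is the reader's idea of the trial's sensitivity. Someone weighing a corrected result against Section 15.2 would credit the three-way test with 80% power at f² = 0.056, when the corrected test may have about half that chance of detecting it or a little less. The three-way test also decides which simpler models are examined next.

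**Working it through.** **Inputs.** From Section 15.2: alpha = .05, power .80, n = 200 or 160, 12 covariates, and the F test for the three-way increment. From Section 5.2: three conditions. From Section 5.1: puberty as a continuous variable.

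**Degrees of freedom.** The numerator is u = 2 × 1 × 1 = 2. The design terms are condition 2, sex 1, puberty 1, condition × sex 2, condition × puberty 2, sex × puberty 1 and three-way 2, in total 11. With 12 covariates and the intercept, v = n − 12 − 11 − 1 = n − 24, that is 176 or 136.

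**Formula.** The test is noncentral F with λ = f²(u + v + 1), as in the pwr library. Power = P[F(u, v, λ) > F crit at the chosen alpha].

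**Step 1: reproduce the plan's figures at alpha = .05.**
- n = 200: λ = 0.056 × 179 = 10.02 and power is 80.9%. The f² for 80% power is 0.0548.
- n = 160: λ = 0.070 × 139 = 9.73 and power is 79.5%. The f² for 80% power is 0.0709.

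A cruder count (u = 3, v = n − 4) gives 0.0556 and 0.0699, which round exactly to the stated values. On either count, the figures match at an unadjusted .05.

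**Step 2: number of outcomes.** The plan does not fix m. Three sizes are carried forward: 6 (one imaging domain), 12 (6 + 6 imaging variables) and 16 (12 plus four physiological measures, one variable each).

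**Step 3: lone effect, threshold alpha/m (u = 2, v = n − 24).** This is the lower bound on BH power.

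| m | n = 200: power at 0.056 | n = 200: f² for 80% | n = 160: power at 0.070 | n = 160: f² for 80% |
|---|---|---|---|---|
| 6 | 57.6% | 0.082 | 55.4% | 0.107 |
| 12 | 48.6% | 0.093 | 46.3% | 0.121 |
| 16 | 45.0% | 0.097 | 42.7% | 0.126 |

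**Step 4: BH step-up by simulation** (q = .05, independent outcomes, 40,000 replicates; average power per affected outcome).

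| m | Affected | n = 200, f² = 0.056 | n = 160, f² = 0.070 |
|---|---|---|---|
| 6 | 1 / 3 / 6 | 58% / 69% / 78% | 56% / 67% / 76% |
| 12 | 1 / 6 / 12 | 49% / 68% / 78% | 47% / 66% / 76% |
| 16 | 1 / 8 / 16 | 46% / 68% / 78% | 43% / 66% / 76% |

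With outcomes correlated at 0.5, the all-affected figures for m = 12 fall to about 75% and 73%. The lone-effect figures barely move.

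**Step 5: size of the covariate cushion.** Dropping all 12 covariates (v = n − 12) lowers the unadjusted f² at n = 200 from 0.0548 to 0.0513, a change of 0.0035. The lone-effect threshold for 12 outcomes raises it from 0.0548 to 0.093, a change of about 0.038.

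**Step 6: the targeted sample.** At n = 150 (v = 126) the f² for 80% power is 0.0765 unadjusted. At alpha/m it is 0.116, 0.131 and 0.137 for 6, 12 and 16 outcomes.

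**The case against.** **Scope of the correction.** The plan never says that BH runs across all primary outcomes. Because Tukey covers the pairwise contrasts, that is the natural reading, but BH within a domain is also open. A count of at least 16 outcomes is an inference: Section 3.1 lists four brain regions and four physiological measures, and Section 15.1 speaks of both 5 and 6 regions. This stands, and it is why the result is given as a range.

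**The mild end.** If every outcome carries the effect, the loss is only about 3 points at either sample size (80.9% to 78%, and 79.5% to 76%). With no covariates and all outcomes affected, simulated power stays at about 81%. So a reader who infers that 80% power is lost in every case goes too far.

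**Harm.** One might infer that a null result will be taken to exclude f² = 0.056. No section says so.

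**Not an arithmetic error.** Section 15.2 discloses its alpha, and its figures reproduce. Powering a single test at .05 is sound for a sole primary outcome. This plan names no sole primary, and it presents the figure as power for the primary analyses.

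**The hypotheses.** Hypotheses 1 and 2 concern condition and puberty, while sex differences are a secondary exploration. The figures here are for the three-way test that Section 15.2 chose; the loss for the two-way tests is not quantified.

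**The word conservative.** The plan ties it to the covariate count and imputation. That supports qualifying the word as an alternative to deleting it, but as written it is attached to the primary analyses without limit.

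**Conclusion.** The point holds as a mismatch between the power assumption and the decision rule. The stated effects match 80% power at an unadjusted .05. With the plan's 12 covariates, power at those effects is below 80% in every BH scenario run: about 46% to 78% at n = 200 and 43% to 76% at n = 160. The lone-effect detectable f² is 0.082 to 0.097 instead of 0.056, and 0.107 to 0.126 instead of 0.070. The direction is firm. The size rests on assumptions that the plan leaves open: the BH family (6, 12 or 16 outcomes), q = .05, the number of affected outcomes and their correlation. The covariate cushion is far smaller than the lone-effect cost of the correction, so the unqualified description as conservative is not supported. The gap exists at the plan's own 200 and 160, so it is separate from the question of which sample size applies.

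**What to change.** 1. In Section 15.3, state the BH family (which outcomes, and whether one family or one per domain) and q.
2. In Section 15.2, restate the detectable f² as a range: the lone-effect case at alpha/m, and one stated case with several real effects.
3. Do this at the sample size that the plan targets. Sections 5.1, 10.1 and the missing-data paragraph of 15.3 give 150, where the lone-effect f² is about 0.116, 0.131 or 0.137 for 6, 12 or 16 outcomes, before any loss of scans.
4. Remove the word conservative, or limit it to the covariate count.

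An unadjusted .05 can stay only if one outcome is named as the sole primary.

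The cost is one recalculation and a few sentences. The stated detectable effect becomes less favourable. Design and data collection do not change.

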4.2 Drug/Device Handling: N/A

4.3 Biosafety: N/A

4.4 Stem Cells: N/A

5.0 Procedures Involved

5.1 Study Design: The study design is cross-sectional. 150 target children (10- to 15-year-olds) will be randomly assigned to one of three conditions: (1) no social support (standard MRI scanning condition); (2) presence of a parent; or (3) presence of a close friend. Outcome measures will be compared across the three social buffering conditions. Pubertal stage will be included as a continuous variable in analyses of physiological and/or brain responses.

Two tasks will be used during the MRI scanning. Both have been shown to activate stress-related regions of the brain in past studies and have been used by our labs. The order of these two tasks will be counterbalanced.

Based on the results of piloting social buffering will EITHER be done with the presence of a buffer in person, or, displayed on screen via a live Zoom feed. All conditions will use the same modality.

Study Overview:

Visit 1: Parent and child will participate in an online video session (via Zoom) lasting approximately 2 hours. Following a detailed overview of study and consent/assent procedures, participants will be asked to complete the following measures:

Parent:

- Questionnaire regarding family income, education level, and family composition
- Parent-report questionnaire about child's general health, behavior, and development (MacArthur Health Behavior Questionnaire; HBQ)
- Parent-report MRI safety screening questionnaire about the child to rule out any contraindications for MRI scanning
- *[If the child is randomized to the parent-present buffering condition],* self-report MRI safety screening questionnaire to rule out any contraindications for sitting in the MRI area

PROTOCOL TITLE: An MRI Study of Learning and Social Support

VERSION DATE: v.10 2024.12.18

- Child life challenges question

Children/adolescents:

- Questionnaire about general health, behavior, and development (MacArthur Health Behavior Questionnaire; HBQ)
- Questionnaire about their relationships with their parents and their best friend (Network of Relationships Questionnaire)
- Questionnaire about anxiety in different contexts (State-Trait Anxiety Inventory for Children)
- Pubertal development questionnaire (Morris and Udry, 1980)
- Safety screening questionnaire to confirm safety in the MRI scanner
- Perceived stress questionnaire
- Child life challenges questionnaire

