10.0 Local Number of Participants

10.1 Local Number of Participants to be Consented: We plan to analyze data from at least 150 target participants. Of these, 50 will bring friends as social buffers. Thus, we plan to enroll at least 200 children. To account for attrition between sessions/replacement for incomplete data, up to 300 children may be consented/enrolled.

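### The power analysis assumes 200 analysed children (160 for imaging), but the plan commits to 150; at 150 the power for f² = .056 is about 66%, not 80%

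*Combined protocol and SAP*

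**What the plan says.** Section 15.2 is the sample-size justification for the primary analyses. It uses R's pwr library with n = 200, alpha .05, power .80 and 12 covariates. The effect tested is the interaction of condition, sex and pubertal stage, and the stated minimum detectable effect size (MDES) is f² = .056. Imaging is handled in one step: "With a sample size of 200, even if we lose 40 of the participants to movement artifact for the imaging analyses", which leaves 160 and an MDES of .070. Section 15.3 describes the mediation simulation as 27 effect-size conditions, "which we examined at our target sample size of 200".

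The design sections give a different number:

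- Section 5.1: "150 target children (10- to 15-year-olds) will be randomly assigned to one of three conditions".
- Section 10.1: "We plan to analyze data from at least 150 target participants. Of these, 50 will bring friends as social buffers". The 200 children it then plans to enrol are these two groups added together. The section continues: "To account for attrition between sessions/replacement for incomplete data, up to 300 children may be consented/enrolled".
- Section 15.3, on missing data: because children who miss session 2 are replaced, "we should have 150 completed participants". The next sentence adds: "Missing data, however, could arise from problems in obtaining good imaging data".

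Section 15.3 also makes the three-way test the first step of the primary analysis: "If the three-way interaction is not significant, we will then examine all two-way interactions".

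**The concern.** The n in the power analysis is not the n of the study. The friends act as buffers and complete a relationship questionnaire. They give no imaging, cortisol or physiological outcome, so they cannot count towards 200. No section plans 200 analysed target children. For imaging, the whole committed sample of 150 is already below the 160 that Section 15.2 assumes are left after motion losses.

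The three-way test decides which model is examined next. If a real three-way effect is missed, the analysis moves to two-way models that leave it out. Readers of 15.2 would believe that risk is 20% at f² = .056 when it is about one in three.

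Three smaller statements are tied to the same justification:

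- Multiple imputation is offered as one reason why the estimate is on the safe side.
- f² is read directly as a percentage of variability.
- Section 15.1 still mentions four buffering conditions.

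**Working it through.** **Inputs.** Alpha .05, power .80, 12 covariates, the pwr library and the three-way test come from 15.2. Three conditions, pubertal stage as a continuous variable and 150 targets come from 5.1.

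**Model.** With three conditions, the main effects take 2 + 1 + 1 = 4 df, the two-way terms 2 + 2 + 1 = 5, and the three-way term 2. So u = 2, the number of predictors is 12 + 4 + 5 + 2 = 23, and v = n − 24.

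**Formula (pwr convention).** λ = f²(u + v + 1). Power = P[F′(u, v, λ) > F(.95; u, v)], where F′ is the noncentral F.

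**Step 1: reproduce the plan's figures.**

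- n = 200: λ = .056 × 179 = 10.02; power 80.9%; MDES .0548.
- n = 160: λ = .070 × 139 = 9.73; power 79.5%; MDES .0709.

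Both are close to the plan. No u = 2 setting tried rounds to both .056 and .070, but two u = 3 settings do:

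- u = 3, v = n − 4, pwr λ: .0556 and .0699.
- u = 3, v = n − 28, λ = f²n: .0558 and .0702.

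Three numerator df is what four conditions would give, which fits the leftover mention of four conditions in 15.1. That origin is an inference; the documents do not state it.

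**Step 2: the committed n of 150.** For u = 2, λ = .056 × 129 = 7.22.

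| Setting | Power for f² = .056 | MDES at 80% |
|---|---|---|
| u = 2, v = n − 24 | 65.9% | .0765 |
| u = 3, v = n − 4 | 66.5% | .0747 |
| u = 3, v = n − 28, λ = f²n | 66.2% | .0751 |

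The miss rate is therefore 100 − 66 = 34%, against 20% as planned.

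**Step 3: sensitivity at n = 150.**

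- No covariates (u = 2, v = n − 12): power 70%, MDES .070. Fewer covariates help, but do not restore 80% at .056.
- The widest settings tried: 73% and .066 (u = 2, v = n − 3), and 58% and .089 (u = 3, v = n − 28, pwr λ). At n = 200 these give .049 and .063, so neither is the calculation behind the stated .056.

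**Step 4: imaging (u = 2, v = n − 24, pwr λ).** The plan gives no loss from 150, so these n are assumptions.

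| Imaging n | Basis | Power for f² = .070 | MDES at 80% |
|---|---|---|---|
| 150 | every motion loss replaced | 76% | .077 |
| 120 | 20% lost, as 40/200 | 64% | .100 |
| 110 | 40 lost | 59% | .112 |

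With u = 3, v = n − 4, the powers are 77%, 66% and 62%.

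**Step 5: reading f² as a percentage.** Partial R² = .056/1.056 = 5.3%. The added R² is this times (1 − R² of the reduced model). It is 5.3% only if the other terms explain nothing; if they explained 30%, for illustration, it would be .053 × .70 = 3.7%.

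**Mediation.** The simulation's parameter values are not given, so its power at 150 cannot be recomputed. Only the mismatch in n is confirmed.

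**The case against.** The strongest reply is that the arithmetic in 15.2 is sound for its own n, and that f² = .056 is a detectable effect, not one the trial has promised to find. The plan describes its MDES as lying between small (.02) and medium (.15). That remains true at .077, .100 and .112. Section 10.1 also says at least 150, allows replacement for incomplete data and sets a ceiling of 300, so more than 150 could be analysed. This is fair as far as it goes. The fault is an inconsistent n, not a miscalculation, and the qualitative description survives. But 150 is the only analysed number the plan commits to, and the stated figures do not describe it.

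Second, one convention is more favourable for imaging. With λ = f²n and u = 2, power for .070 at n = 150 is 82.5%. That setting gives .049 at n = 200 rather than .056, so it is not the plan's calculation. The statement that .070 is out of reach at 150 should nevertheless be limited to the pwr convention with 12 covariates; with no covariates, power at 150 is just 80%.

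Third, these powers are for a single test at alpha .05, before the Benjamini-Hochberg correction in 15.3. That qualifies the planned 80% equally and does not rescue it.

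Fourth, imputation of missing outcomes, which 15.3 allows, can recover some information through related variables. It cannot raise the sample above 150, and it sits awkwardly with 15.1, which excludes participants with more than 25% of data points censored.

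**Conclusion.** The concern holds. Sections 15.2 and 15.3 rest on 200 analysed children, while the rest of the plan provides for 150. At 150, power for f² = .056 is about 66%, and the MDES is about .075 to .077. This rests on the noncentral F test at uncorrected alpha .05. It is the same under the three-condition model and under the settings that reproduce the plan's figures. The imaging shortfall (76% at best, 64% at a 20% loss, for f² = .070 in the 12-covariate pwr model) depends on an imaging n that the plan does not state. How far mediation power falls cannot be determined from the documents. The correction is needed because 15.2 is the only sample-size justification for the primary analyses.

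**What to change.** Choose one n and use it throughout.

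**Option 1: keep 150.** In 15.2, restate the MDES for three conditions at n = 150 (about .077, or 66% power for f² = .056) and at a declared imaging n (.077 at 150, .100 at 120, .112 at 110). State u and v, and say whether children lost to motion are replaced. The cost is rewording in 15.1 to 15.3 and a rerun of existing code. The published figures become less favourable, and no extra participants are needed.

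**Option 2: analyse 200 targets.** Say so in 5.1, 10.1 and 15.3. With one friend per three targets this is 200 + 200/3 ≈ 267 children, about 50 more targets and 17 more friends. The ceiling of 300 leaves 33 children. At the same ratio 300 children hold 225 targets, so about 25 replacement targets.

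**Under either option:**

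- Rerun the mediation simulation at the chosen n.
- Drop multiple imputation as a reason for calling the power estimate conservative; the covariate reason can stay.
- Describe f² as a ratio to residual variance.
- Change four conditions to three in 15.1.

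### Section 15.2's promise of larger power for the two-way and main-effects models holds model by model at unadjusted alpha, but not for the sequential, BH-corrected procedure of Section 15.3

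*Combined protocol and SAP*

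**What the plan says.** Section 15.2 of the combined protocol and SAP computes a minimum detectable effect for the condition × sex × puberty interaction at n = 200, alpha .05, power .80 and 12 covariates: "we should be able to detect an f^2 of 0.056". Allowing for imaging losses it adds, for "a sample size of 160, we will still have an f^2 of .070". The tool is named: "Power was estimated in R (R Core Team) using the pwr library". The section calls its estimate conservative and closes by saying that for the two-way and main-effects models "the power will be larger than these reported values as the models will be simpler".

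Section 15.3 then sets the order of testing. The three-way term comes first: "If the three-way interaction is significant, we will not examine any other model". If it is not significant, the two-way terms are examined. Then: "If the two-way interactions are not significant, we will then examine main effects only models". On multiplicity: "We will correct for multiple comparisons using the Benjamini-Hochberg (BH) correction". The plan does not say which outcomes form the BH family, whether BH also decides the preceding tests, or whether the two-way terms are tested singly or as a block.

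**The concern.** The closing sentence of Section 15.2 counts only the few residual degrees of freedom that a simpler model saves. Under Section 15.3 the simpler models are not always run. Each is reached only if the tests before it are non-significant, and those tests have their own false-positive rate. The final decision is also taken after BH, while the calculation uses alpha .05.

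The terms affected matter. Hypotheses 1 and 2 in Section 2.3 concern condition effects that wane with puberty, so the 2-df condition × puberty term and the condition main effect are the central tests. The closing sentence is the only statement in the plan about the power of these regression terms, and it tells the reader that power exceeds 80%.

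**Working it through.** **Inputs.** Three conditions (2 df), sex (1 df) and continuous puberty (1 df) give 4 main-effect df, 2 + 2 + 1 = 5 two-way df and 2 three-way df. With 12 covariates and n = 200, the residual df are:
- three-way model: v = 200 − (12 + 4 + 5 + 2) − 1 = 176
- two-way model: v = 200 − (12 + 4 + 5) − 1 = 178
- main-effects model: v = 200 − (12 + 4) − 1 = 183

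**Formula.** Power is the upper tail of a noncentral F(u, v) beyond the 5% critical value, with the pwr convention λ = f²(u + v + 1).

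**Step 1: the plan's own figures.** With u = 2 and v = 176, power at f² = 0.056 is 0.809 (80% power is reached at f² = 0.0548). At n = 160, v = 136 and f² = 0.070 it is 0.795. Both agree with the stated 0.80.

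**Step 2: each simpler model by itself, alpha .05.**

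| Term | u, v | n = 200, f² = 0.056 | n = 160, f² = 0.070 |
|---|---|---|---|
| Three-way | 2, n − 24 | 0.809 | 0.795 |
| Condition × puberty | 2, n − 22 | 0.814 | 0.801 |
| Condition main effect | 2, n − 17 | 0.825 | 0.816 |
| All two-way terms jointly | 5, n − 22 | 0.677 | 0.661 |

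The gain for the 2-df terms at n = 200 is 0.5 to 1.6 points. The joint 5-df test is weaker than the three-way test (detectable f² 0.072), so on that reading the sentence fails even without the sequence.

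**Step 3: the Section 15.3 sequence, uncorrected .05 at every step, no true higher-order effect** (n = 200, f² = 0.056):
- Condition × puberty after the three-way test: 0.95 × 0.814 = 0.773.
- Same, if the two-way terms must pass the joint 5-df test: 0.95 × 0.677 = 0.643.
- Condition main effect, two-way terms tested jointly: 0.95 × 0.95 × 0.825 = 0.745.
- Condition main effect, three two-way terms tested singly, any of them blocking: 0.95 × 0.95³ × 0.825 = 0.672.

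Simulating the whole sequence (12,000 replicates) gives 0.770 for the first, 0.745 for the third and 0.672 for the fourth. At n = 160 and f² = 0.070 the four products are 0.76, 0.63, 0.74 and 0.66.

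**Step 4: BH at every step.** The family is an assumption: 6 task and 6 connectivity variables (Section 15.1) plus cortisol, heart rate, respiration and skin conductance (Section 3.1), 16 in all.
- The strictest BH level is .05/16 = 0.003125. Passing four null tests at that level has probability (1 − 0.003125)⁴ = 0.988, so the sequence costs about 1 point.
- Power of the final test at that level, with the sequence included, is 0.455 for condition × puberty and 0.468 for the condition main effect.
- Simulating BH at all steps gives about 0.46–0.49 if one outcome carries the effect and about 0.78–0.79 if all 16 do.

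**Step 5: sensitivity.** With 0 to 6 covariates at n = 200, the Step 3 figures (single-term test for condition × puberty) range from 0.68 to 0.80, while the three-way power itself rises to 0.82–0.84. With λ = f²n instead of the pwr convention, condition × puberty is about 0.81 and the main effect 0.68–0.77. The stated three-way benchmark would rise under that convention too, and it is not the one the plan used.

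**The case against.** The strongest reply is that Section 15.2 speaks of models, gives simplicity as its reason, and is right on those terms. That stands: a reader might infer an arithmetic error in the per-model figures, and there is none. What fails is carrying the per-model figure over to a procedure that does not run those models unconditionally.

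Three further points limit the conclusion.
- A reader might infer that null results would be over-read. That does not follow. The sequence is cut short only when a higher-order term is significant, and a main-effect null is seen only when that model is reached, where power at uncorrected .05 is still about 0.82. Section 15.3 also triggers pairwise comparisons when condition is significant as an interaction, so a true condition main effect is flagged in some form about 0.82 of the time. What is lost is detection at its own step.
- A reader might add the sequence loss to the BH loss. The large sequence loss needs uncorrected preceding tests; if BH governs them, it nearly vanishes.
- The figure of about 0.46 is not a general BH figure. It belongs to the least favourable case of a family that the plan does not define.

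The 0.67 also needs any single two-way term, including sex × puberty, to block the main-effects model. Section 15.3 does not say this, which is why both readings are shown.

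**Conclusion.** Wrong as written for the procedure that will be run; correct only per model at unadjusted alpha .05. At n = 200, f² = 0.056, 12 covariates and the pwr convention, no reading worked through above that applies one significance rule throughout the sequence gives the two condition terms more than 0.80. With uncorrected tests, condition × puberty has about 0.77, or 0.64 under a joint two-way test, and the condition main effect 0.67 to 0.745. With BH throughout and 16 outcomes, the range is about 0.46 to 0.79.

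The uncorrected figures assume that higher-order terms are truly zero; a real one would stop the sequence more often. The conclusion covers the 2-df condition terms only: the 1-df sex × puberty term, tested singly, keeps about 0.84 after the three-way test at uncorrected .05. It does not show that the order of testing or the sample size is wrong.

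**What to change.** In Section 15.2, limit the closing sentence to what it supports: the gain is per model, at unadjusted alpha .05, and unconditional on the Section 15.3 sequence. Beside it, state the simulated power of condition × puberty and of the condition main effect under that sequence, with BH as it will actually be applied. Name the assumptions: the outcome family, the level used at each preceding test, whether the two-way terms are tested singly or jointly, and how many outcomes are taken to carry the effect.

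Run it at the n planned for analysis. Sections 5.1, 10.1 and the missing-data paragraph of 15.3 refer to 150, not 200. At n = 150 and f² = 0.056, the uncorrected sequential figures are about 0.63 for condition × puberty (single-term test) and 0.56 to 0.62 for the condition main effect.

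The cost is SAP wording and one short simulation. The downside is that the stated power becomes less favourable. The design, test order and sample size need not change on account of this point.
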